# 5.3.2 Functional Assessment of Chronic Illness Therapy (FACIT) Fatigue Scale

The FACIT Fatigue Scale (Version 4) is an exploratory efficacy endpoint. The individual fatigue score will be calculated as 0-52 (see Section 17.1 of the protocol), where a higher score corresponds to a higher quality of life.

Individual fatigue scores will be listed along with changes from baseline for the ITT Set at each scheduled visit. Study Day 1 will be considered the baseline for the FACIT assessment. If this is missing, change from baseline will not be calculated.

The fatigue score, changes from baseline, and percent changes from baseline will be summarized, using descriptive statistics (mean, SD, median, minimum, and maximum), by randomized dose group and by cohort at each scheduled study visit for both Part A and Part B of the study.

All individual fatigue scores will be plotted by actual study day, where each subject will be identifiable. The mean score  $\pm$  SE for each scheduled visit by dose group and cohort will also be plotted. Individual scores and mean changes from baseline  $\pm$  SE will also be plotted similarly.

The FACIT and all related works are owned and copyrighted by, and the intellectual property of **PPD** Ph.D. Permission for use of the FACIT-FATIGUE questionnaire is obtained by contacting **PPD** at [contact].

## 5.3.3 Linear Analog Self-Assessment (LASA)

The LASA, which consists of five single statements asking respondents to rate, on zero to ten scales, their perceived level of functioning (see Protocol Section 17.2).

Specific domains include physical well-being (i.e., fatigue, activity level), emotional well-being (i.e., depression, anxiety, stress), spiritual well-being (i.e., sense of meaning), and intellectual well-being (i.e., ability to think clearly, concentrate). An item for overall quality of life (QoL) is also included. The Likert scales run from 0 (as bad as it can be) to 10 (as good as it can be), where higher ratings suggest higher QoL.

Individual domain scores and the overall QoL domain score will be listed along with changes from baseline for the ITT Set. Study Day 1 will be considered the baseline for the LASA assessments. If this is missing, change from baseline will not be calculated.

The scores, changes from baseline, and percent changes from baseline for the five domains will be summarized, using descriptive statistics, by randomized dose group, by cohort, and overall at each scheduled study visit for both Parts A and B of the study.

All individual LASA scores will be plotted by actual study day, where each subject will be identifiable. The mean score  $\pm$  SE for each scheduled visit by dose group and cohort will also be plotted. Individual and mean changes from baseline  $\pm$  SE will also be plotted similarly.

## 5.3.4 Efficacy Laboratory Parameters

Efficacy laboratory parameters include the following:

- 1. Hemoglobin
- 2. Lactate Dehydrogenase
- 3. Reticulocytes
- 4. Haptoglobin
- 5. Indirect Bilirubin

Individual data will be listed by along with changes from baseline and percent changes from baseline.

Results, changes from baseline, and percentage changes from baseline will be summarized, using descriptive statistics, at each scheduled study visit by randomized dose group and cohort, in addition to overall.

All individual results will be plotted by actual study day, where each subject will be identifiable. The mean results  $\pm$  SE for each scheduled visit by dose group and cohort will also be plotted. Individual and mean changes from baseline  $\pm$  SE will also be plotted similarly.

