## Efficacy Endpoints:

- Change from baseline in Hb
- Number of red blood cell (RBC) transfusions during study
- Change from baseline in absolute reticulocyte count
- Change from baseline in LDH
- Change from baseline in haptoglobin
- Change from baseline in indirect bilirubin
- APL-2 serum concentrations (and pharmacokinetic (PK) parameters as appropriate
- Change from baseline in Functional Assessment of Chronic Illness Therapy (FACIT) scale and the Linear Analog Scale Assessment scale (LASA) including energy level, ability to perform daily activity, and overall quality of life (QoL)

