## 4.1.2 Visit Windowing Based on Study Day

Data will be summarized and analyzed based on the list of visits specified in table below for the Part A Core Study Phase. The relative day will be used to assign analysis visit following the table below. All the records post-baseline will be assigned to an appropriate analysis visit using the following:

For the post-baseline visits, the lower and the upper bound for the analysis visit windows are defined as the midpoints of the target date of the scheduled visits. If the date of assessment falls in between the lower bound and the upper bound for a visit as specified in the schedule of assessments of the protocol, then it will be assigned to that visit. If the interval separating 2 scheduled visits is an even number of days, the middle day will be included in the lower bound of the next visit. If more than 1 record is within the same analysis visit window, the record closest to the midpoint of the interval will be used in the analysis. If 2 records are tied before and after the middle of the interval, the earlier record will be used in the analysis. If more than one assessment (including the early termination or

unscheduled assessments) falls within the same defined window, the assessment closest to the target day with non-missing data will be considered for analysis.

In listings that are presented by visit, windowed assessments that are used in the analysis tables by visit will be identified.

Part	Study Visit	Target Day	Analysis Window	Interval
Core	1	-30	<1*	NA
Study	2	1	1	1
(Part A)	3	2	2	1
	4	3	3	1
	5	7	>=4-<11	7
	6	14	11-<21	10
	7	28	21-<42	21
	8	56	42 - <70	28
	9	84	70 - < 98	28
	10	112	98 - < 126	28
	11	140	126 - < 154	28
	12	168	154 - < 196	42
	13	224	196 - < 252	56
	14	280	252 - < 308	56
	15	336	308 - < 364	56
	16 (FU)	378	364 - < 399	35
	17 (Exit)	420	399 - < 441	42

\*Must be prior to dosing if time of assessment is recorded.

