## 4.1.3 Baseline and Change from Baseline

In general, the baseline for this study (with the exception of physical examination) will be taken as the latest pre-dose measure on Study Day 1 (i.e. prior to the first dose for all cohorts). If this is missing then the screening value, or, if available, a pre-dose unscheduled measurement will be used (whichever is closer to the baseline date). For physical

examination, the baseline assessment will be considered as the Screening Visit 1.

Unless indicated otherwise change from baseline (CFB) will be calculated as follows:

CFB = Visit Result – Baseline Result

Percent change from baseline (PCFB) will be calculated as follow: PCFB (%) = 100\*(Visit Result – Baseline Result)/Baseline Results

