## 5.3.1 Red Blood Cell (RBC) Transfusions

The absolute and change in number of RBC transfusions per month will be tabulated using descriptive statistics by randomized dose group, by cohort, by phase of the study (Baseline, Part A Core Study Phase and Part B Long Term Extension Phase) and over the whole on-treatment study parts (Part A and Part B combined).

Summary statistics will be presented by study phase as follows:

- Baseline:
  - Number of Transfusions and Units per month for the *n* subjects who had at least 1 infusion in the 365 days prior to first study dose
  - Number of Transfusions and Units per month for the N subjects in the dose group (i.e. all subjects in the dose group, regardless of receiving transfusions prior to enrollment)
- Post-Baseline Study Phases (Part A, Part B, Part A and B combined):
  - Number of Transfusions and Units per month for the *n* subjects who had at least 1 infusion in the respective phase
  - Number of Transfusions and Units per month for the N subjects in the dose group (i.e. all subjects in the dose group, regardless of receiving transfusions during the respective phase)
  - Change from Baseline of the Number of Transfusions and Units for the N subjects in the dose group (i.e. all subjects in the dose group, regardless of receiving transfusions during the respective phase)

Only whole blood and Packed Red Blood Cell (PRBC) transfusions will be included.

The number of RBC transfusions per month will be calculated for each part of the study as:

RBC transfusions per month

number of transfusion reported during study part \* 28 number of days in that part of study

The whole on-treatment study will be from first dose to last dose received. A similar calculation will be used for the number of units transfused per month.

The baseline number of transfusions per month will be calculated as number of transfusions reported on 12-month transfusion history /12.

All 12-month transfusion history and on study transfusion data will be listed by Cohort. A separate listing of the number of transfusions per month and number of units transfused per month for baseline, each part and over the whole on-treatment study parts will also be included.

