### Part A + B Lab Results:

- Lab results at all scheduled visits through Part A Visit 15 and from Part B Baseline through end of study
- Change from Part A + B Baseline lab result at all post-baseline visits through Part A Visit 15 and from Part B Baseline through end of study
- Percent Change from Part A + B Baseline lab result at all postbaseline visits through Part A Visit 15 and from Part B Baseline through end of study

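### Both SAPs summarise Hb by visit without regard to recent RBC transfusion, so small-group mean changes can include donor-cell Hb; a supplementary summary that accounts for this should be prespecified

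*SAP*

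**What the plan says.** Protocol 8.2 lists "Change from baseline in Hb" and "Number of red blood cell (RBC) transfusions during study" as separate efficacy endpoints, without ranking them and without a transfusion condition on Hb.

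- **Hb, Part A SAP 5.3.4.** "Results, changes from baseline, and percentage changes from baseline will be summarized, using descriptive statistics, at each scheduled study visit". The tables are split by assigned dose, by cohort and for all subjects together, and individual plots and mean ± SE plots are also planned.
- **Hb, Part B SAP 5.3.4.3 and 5.3.4.4.** The same statistics by cohort, for example "Change from Part A + B Baseline lab result at all post-baseline visits through Part A Visit 15", with mean ± SE figures.
- **Baseline.** Part A SAP 4.1.3: in general baseline "will be taken as the latest pre-dose measure on Study Day 1", with a screening or unscheduled pre-dose value as back-up. Part B SAP 4.2.2 uses the last value before the first dose for the combined analysis, and the last value before the first 1,080 mg dose for Part B.
- **Choice of value within a visit window.** Part A SAP 4.1.2: "the assessment closest to the target day with non-missing data will be considered for analysis". Unscheduled values are eligible. Part B SAP 4.2.3 also selects on an evaluable result and its date, then prefers central over local laboratory.
- **Transfusions, Part A SAP 5.3.1.** "The absolute and change in number of RBC transfusions per month will be tabulated using descriptive statistics". In addition, "All 12-month transfusion history and on study transfusion data will be listed by Cohort". Part B SAP 5.3.1 gives rates per month and listings. Neither section is linked to the Hb tables.

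**The concern.** Hb measured soon after a transfusion includes donor cells. If that value is the one nearest the target day, it enters the visit mean as though it were the subject's own change on APL-2. Transfusion tends to follow a low Hb, so on study the upward error falls mainly on subjects who are doing poorly. A transfusion shortly before Day 1 raises baseline and makes the later change look smaller. The same can happen at the Part B baseline.

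Transfusions are to be expected. Subjects enter with Hb below 11 g/dL (Protocol 10.1), the protocol hopes to reduce transfusion dependency (7.3), and transfusions are counted as an outcome. The transfusion tables report rates over whole study phases, so they cannot show which visit means contain affected values.

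At stake is how the Hb summaries are read. Protocol 7.1 says the efficacy assessments will help guide further development, and 7.2.1 gives identifying an optimal dose as a reason for including both 270 and 360 mg/d.

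**Working it through.** **1. Is there a rule anywhere?** The places where one could sit:

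- Missing data (Protocol 15.2.6; Part A SAP 4.4; Part B SAP 4.4): dropouts, missing baselines, dates and quantification limits. Transfusion is not mentioned.
- Per Protocol Set (Part A SAP 4.2; Part B SAP 4.1): removes eligibility violations and protocol deviations. Transfusion is not called a deviation.
- Pre-lock data review (same sections): a general power to resolve data problems, with no criterion for transfused subjects.
- Windowing: Part A windows for Visits 5 to 15 are 7 to 56 days wide, so an unscheduled Hb check after a transfusion can become the visit value.

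No visible text excludes, replaces, flags or runs a sensitivity analysis on Hb values after transfusion.

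**2. Size.** The plan states no Hb effect size, SD or power, so there is no figure of its own to reproduce. Inputs:

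- n = 6 per dose group within cohort and 12 per cohort (Protocol 11.3.2; both are maxima).
- d = residual Hb uplift per unit. Assumption, not in the documents: 0.5, 1.0 or 1.5 g/dL.
- k = subjects with a recently transfused value at the visit, u = units each. Neither is given in the documents.

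Shift in visit mean = k × u × d / n.

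- k = 1, u = 1, n = 6: 0.5/6 = 0.08; 1.0/6 = 0.17; 1.5/6 = 0.25 g/dL.
- k = 1, u = 1, n = 12: 0.5/12 = 0.04; 1.0/12 = 0.08; 1.5/12 = 0.125 g/dL.
- k = 2, u = 2, n = 6 (a heavier scenario that nothing in the documents establishes): 4 × 0.5/6 = 0.33; 4 × 1.0/6 = 0.67; 4 × 1.5/6 = 1.00 g/dL. At n = 12 these halve to 0.17, 0.33 and 0.50.
- k = 0: no shift.

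A transfused baseline moves the mean change by the same amount in the opposite direction.

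**3. Which handling helps?** Take six subjects: four with a true change of +2.0 g/dL, and two non-responders with a true change of 0 who were recently transfused, uplift 1.0 g/dL each.

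- True mean: (4 × 2.0 + 2 × 0)/6 = 8/6 = 1.33.
- As observed: (8 + 2 × 1.0)/6 = 10/6 = 1.67, too high by 0.33.
- Post-transfusion values set to missing: 8/4 = 2.00, too high by 0.67.
- Replaced by the last Hb before the transfusion: 8/6 = 1.33 if that value equals baseline. If it lies x g/dL below baseline, (8 − 2x)/6, which is lower than 1.33.

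So deletion is worse than the as-observed mean here, because it removes the two poor responders from the denominator. Replacement keeps them in.

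**The case against.** The case for leaving the plan alone has several sound parts.

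- **Exploratory and descriptive.** The primary endpoints are safety. Both SAPs (5.3) call the efficacy analyses exploratory and (4.3) rule out formal inference. No decision rule depends on an Hb mean. This stands, and it limits the point to interpretation.
- **Frequency unknown.** Eligibility does not require transfusion dependence, and Protocol 4.1.3 says transfusion in AIHA should be restrictive and that autoantibodies can impair recovery. A full uplift lasting weeks may be unusual. This stands; the sizes above are conditional.
- **Raw data are shown.** Part A plots each subject's Hb, medians accompany means, and transfusions are listed, so with up to 24 subjects a hand cross-check is possible. That is partial mitigation. In the example above the median is 2.0 with or without the uplift. But the means and mean plots stay mixed, and the visible Part B Hb figures are means only.
- **Data review before lock.** It could deal with such values, but in an open-label study that would be a choice made with the data in view.
- **Not everything is visible.** The planned-output appendix and table shells cannot be seen. A footnote there cannot be ruled out, though no visible text points to one.

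A reader might also infer that the trial's lead efficacy marker is compromised, that transfused non-responders will be counted as Hb responders, or that one or two values could create or hide a dose effect. The documents do not support this. No efficacy endpoint is ranked, no Hb responder is defined in the visible text, and a transfusion after a fall in Hb may only mask the decline. One subject with one unit moves a dose-group mean by at most 0.25 g/dL under the assumed range.

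**Conclusion.** The gap holds in both SAPs. Followed as written, the plan admits donor-cell Hb into visit means and mean changes, upward for on-study transfusions and downward for transfusions just before baseline. For one subject with one recent unit, the shift is 0.08 to 0.25 g/dL in a Part A dose group of 6 and 0.04 to 0.125 g/dL in a cohort of 12. This rests on the assumed 0.5 to 1.5 g/dL per unit and on such a value being present at the visit; otherwise the shift is zero.

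Two further inferences should be resisted. The n=6 and 270 versus 360 mg/d argument does not carry over to the Part B SAP, whose Hb tables are by cohort. And deleting post-transfusion values is not a neutral correction, since it selects against the subjects doing worst.

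**What to change.** Keep all planned as-observed tables and figures. In both SAPs, add one supplementary Hb summary and mean plot with these rules:

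- **On study.** Hb values within a prespecified window after a whole blood or PRBC transfusion (for example 28 days, repeated with 14) are replaced by the last Hb before that transfusion, not set to missing. Where windows overlap, use the last value before the first transfusion in the run.
- **Baseline.** Use the last pre-dose value outside the window if one exists. Otherwise keep the Day 1 value and flag it. Apply the same logic to the Part B baseline, where the fallback is the planned value.
- **Reporting.** Give the number of affected values per visit, and mark them in the Hb listings and the Part A individual plots.

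The cost is SAP wording, one table and one figure in each report, and a listing flag. No new data collection should be needed: both SAPs count transfusions in the 365 days before first dose and assign on-study ones to a study part, which implies dates. Check this against the eCRF, because Protocol 12.1 and 13.1.2 mention only the number of prior-year transfusions.

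The downsides are that the window length is a convention, hence two windows, and that carrying the pre-transfusion value forward is conservative because that value tends to be a low point. The result is a companion to the as-observed table, not a substitute for it.

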## 5.3.5 Pharmacodynamics

PD parameters include the following:

- 1. Complement CH50
- 2. Complement AH50
- 3. Complement C3

Individual data will be listed by along with changes from baseline and percent changes from baseline.

Results, changes from baseline, and percentage changes from baseline will be summarized, using descriptive statistics, at each scheduled study visit by randomized dose group and cohort, in addition to overall.

All individual results will be plotted by actual study day, where each subject will be identifiable. The mean results  $\pm$  SE for each scheduled visit by dose group and cohort will also be plotted. Individual and mean changes from baseline  $\pm$  SE will also be plotted similarly.

Additional PD parameters also include the following:

- C3 deposition on RBCs
  - Percent Type I
  - Percent Type II
  - Percent Type III
  - Percent Type I+II
  - Percent C3d on RBC

where:

%C3d on (Type I + II RBCs)

$$= \frac{\begin{pmatrix} C3d \ Type \ I \ RBC \ \% * \ C3d \ Type \ I \ RBC \ Events \ + \\ Type \ II \ RBC \ \% * \ C3d \ Type \ II \ RBC \ Events \ + \\ \hline C3d \ Type \ I \ RBC \ Events \ + \ C3d \ Type \ II \ RBC \ Events \ x \ 100 \\ \end{bmatrix}}{x \ 100}$$

and where:

% C3d on RBC = 
$$\frac{C3d + Gly RBC Events}{Gly + RBC Events} x 100$$

Results, changes from baseline, and percentage changes from baseline will be summarized for each parameter, using descriptive statistics, at each scheduled study visit by randomized dose group and cohort, as well as overall.
Apellis Pharmaceuticals, Inc. Protocol: APL2-CP-AIHA-208 Statistical Analysis Plan

A plot of the mean percentage distribution (Type I, Type II, and Type III)  $\pm$  SE will be plotted by dose group and cohort at each scheduled visit. A different line will specify Type I, Type II, and Type III for each dose group and cohort.

The following will also be plotted at each scheduled visit:

- Percent Type  $I + II \pm SE$
- Percent Type I ± SE
- Percent Type II  $\pm$  SE

All individual results will be plotted by actual study day, where each subject will be identifiable. The mean results  $\pm$  SE for each scheduled visit by dose group and cohort will also be plotted. Individual and mean changes from baseline  $\pm$  SE will also be plotted similarly.

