#### 5.3.5 Pharmacodynamics

#### 5.3.5.1 Parameters

PD parameters include the following:

- 1. Complement CH50
- 2. Complement AH50
- 3. Complement C3

Additional PD parameters also include the following:

- C3 deposition on RBCs
  - Percent Type I
  - Percent Type II
  - Percent Type III
  - Percent Type I+II
  - Percent C3d on RBC

where:

$$%C3d on (Type I + II RBCs) = \frac{\binom{Events (C3d (CD59 HighType1 norm RBC) +}{Events (C3d (CD59 dim Type II RBC)})}{\binom{Events CD59 high Type 1 norm (RBC) +}{Events CD59 dim Type II (RBC)}} x 100$$

and where:

% C3d on RBC = 
$$\frac{C3d + Gly RBC Events}{Gly + RBC Events} \times 100$$

Study Day 1 will be considered the Part A+ B Baseline for the PD assessments. If this is missing, the screening assessment, if available, will be used as Part A + B Baseline. Part B Baseline will be considered as the last assessment before the first 1080mg APL-2 dose for each subject.

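### As printed, the Part A formula for C3d on Type I + II red cells weights by C3d events, so it can exceed the pooled percentage that the Part B SAP defines under the same name

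*SAP*

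**What the plan says.** Two plans define the same derived variable. The SAP dated 27 Apr 2020 (here the Part A SAP) lists C3 deposition on red cells in 5.3.5 and gives a formula for the percentage "C3d on (Type I + II RBCs"). Its numerator has two terms, each a class percentage times a count labelled as C3d events of that class. Its denominator is the sum of those two C3d event counts. The ratio is multiplied by 100. In the second term the percentage is printed as a Type II percentage without the C3d prefix.

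The Part B SAP dated 08 Nov 2022 (5.3.5.1) uses counts only. The numerator adds "Events (C3d (CD59 HighType1 norm RBC") to the matching Type II count. The denominator adds "Events CD59 high Type 1 norm (RBC") and "Events CD59 dim Type II (RBC").

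Both plans give the same companion formula for C3d on all red cells, with "C3d + Gly RBC Events" over all glycophorin-positive red cell events.

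The Part B SAP Introduction states that the 2020 plan was used for the interim Part A analysis. It does not mention that this formula changed.

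**The concern.** A pooled percentage over two cell classes is a weighted mean of the class percentages, with all cells in each class as the weights. The Part A text uses the C3d events as weights instead. If those are the positive cells, each percentage is weighted by its own numerator, and the class with the higher C3d percentage counts for too much.

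C3 deposition on red cells is a named exploratory PD marker in both plans. At stake is whether one sample can carry two values under one name in the interim and final reports, and whether Part A changes from baseline for this variable are on the pooled scale.

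**Working it through.** **Inputs.** The formulas come from the two SAP sections above. Neither plan gives event counts, so every count below is assumed.

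**Notation.** For class i (1 = Type I, 2 = Type II), n_i is all events, c_i is C3d-positive events, and p_i = c_i/n_i as a proportion. N = n1 + n2.

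- Part B SAP: 100 × (c1 + c2)/N.
- Part A SAP, with C3d events read as positives and both percentages as C3d percentages: 100 × (p1·c1 + p2·c2)/(c1 + c2) = 100 × (c1²/n1 + c2²/n2)/(c1 + c2).

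**Direction.** Part A minus Part B, in percentage points, is 100 × n1·n2·(p1 − p2)²/[N·(c1 + c2)]. This is never negative and is zero only when p1 = p2 (or one class is empty). A check on 100,000 random sets of counts found no case with Part A below Part B.

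**Worked case.** Type I: 1,000 positive of 9,000 (11.1%). Type II: 600 positive of 1,000 (60%).

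- Pooled: (1,000 + 600)/10,000 = 16.0%.
- Part A as printed: (0.1111 × 1,000 + 0.60 × 600)/1,600 = 471.1/1,600 = 29.4%.

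**Range over assumed inputs.**

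| Type I : Type II mix | p1 / p2 | Pooled (Part B) | Part A as printed |
|---|---|---|---|
| 90 : 10 | 11.1% / 60% | 16.0 | 29.4 |
| 90 : 10 | 10% / 40% | 13.0 | 19.2 |
| 90 : 10 | 2% / 30% | 4.8 | 19.5 |
| 50 : 50 | 10% / 50% | 30.0 | 43.3 |
| 99.9 : 0.1 | 10% / 50% | 10.04 | 10.20 |
| 95 : 5 | 20% / 20% | 20.0 | 20.0 |

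**Change from baseline.** The excess depends on (p1 − p2)², so it need not cancel between visits. If a subject moved from the second row to the third, the pooled value would fall by 8.2 points (13.0 to 4.8), while the printed Part A value would rise by 0.3 (19.2 to 19.5).

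**When the formulas agree.** If the C3d events are all gated cells of the class, the worked case gives (0.1111 × 9,000 + 0.60 × 1,000)/10,000 = 16.0%, the pooled value. This also needs inputs entered as proportions and the second percentage to mean C3d Type II. If that percentage is instead the Type II share of red cells (10%), the same case gives (1,000 + 0.10 × 1,000)/10,000 = 11.0%.

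**Who is affected.** Part B SAP 5.3.5.3 and 5.3.5.4 report PD results for scheduled visits through Part A Visit 15, with change from the Part A baseline. Section 4.1 makes the PD Set identical to the Safety Set, limited to subjects who roll over and receive at least one 1,080 mg dose. Their Part A samples are therefore already covered by the pooled formula in the final analysis. The interim report, and anyone outside that set, stay on the Part A formula.

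**The case against.** The strongest reply is that the Part A label is undefined. Averaging class percentages with event counts as weights is a valid route to the pooled percentage when the counts are all gated cells, and C3d Type I events could mean Type I cells acquired in the C3d panel. The companion formula prints a plus sign after C3d to mark positives, and the Type I and II weights do not. This stands as a reason for caution, because the documents do not show what the program did. It does not rescue the text. The Part B SAP separates C3d-prefixed events from plain class events for the same variable, and agreement needs three conditions that the Part A SAP does not state.

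A reader might also infer a second error: that multiplying by 100 puts results on a 0 to 10,000 scale (2,944 in the worked case). The documents do not support that. It follows only if inputs are on a 0–100 scale, which is not stated, and the formula is visibly damaged in extraction, with a stray plus sign and the factor of 100 appearing twice. With proportions, one factor of 100 is correct.

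Nor do the documents support the inference that all Part A values stay uncorrected, since the final analysis already re-derives those of the Part B PD Set. The consequence is also limited: one derived variable within an exploratory marker, no inferential testing, and the companion C3d percentage defined identically in both plans.

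**Conclusion.** The point holds for the formula as written. It rests on reading the Part A weights as C3d-positive events and the second percentage as the C3d Type II percentage. On that reading the result is at or above the pooled percentage, with equality only when the two class percentages match. In the assumed cases the excess runs from zero, through 0.16 points when Type II cells are very rare, to 14.7 points (19.5 against 4.8). The true size cannot be known without the counts.

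This shows a stated derivation that gives the wrong value if followed. It does not show that the reported Part A results are wrong, because the program may have used gated counts. The affected results are this variable in the interim Part A report and in subjects outside the Part B PD Set. The primary safety endpoint is untouched.

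**What to change.** Apply the event-count formula in Part B SAP 5.3.5.1 to every Part A subject. Recompute this variable and its changes from baseline, and state the change of formula in the final report. The Part B SAP Introduction already commits that report to discussing deviations.

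First check the Part A program. If it used all gated events as weights, proportions as inputs and the C3d Type II percentage in the second term, the values are right: correct the labels and say so.

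The cost is one formula and a rerun, provided total Type I and Type II counts are held for all Part A samples. The final analysis already needs those counts for the Part A visits of subjects in the Part B PD Set.
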